1.0 Project Summary/Abstract

The ability to promote and support remyelination has wide-ranging implications for a number of neuropsychiatric conditions from multiple sclerosis to major depression. Pre-clinical evidence has demonstrated that thyroid hormone treatment, in the form of triiodothyronine (T3) or tetraiodothyronine (T4), can promote and support remyelination by increasing myelin basic protein mRNA and protein, oligodendrocyte proliferation and maturation, and fractional anisotropy (a diffusion imaging measure of white matter integrity). Pilot data from our own studies suggest that baseline thyroid status is correlated with the integrity of white matter tracts associated with major depression. *To date, the impact of thyroid hormone administration on white matter tracts has not been studied in vivo in adult humans.* The purpose of the proposed pilot study is to examine changes in white matter tract integrity using high angular diffusion imaging and multi-component relaxometry in a population of subjects clinically indicated to receive thyroid hormone for hypothyroidism. We will scan patients with hypothyroidism at the initiation of treatment and at three and six months after starting thyroid hormone treatment. We will also administer scales assessing mood and cognition which have been shown to correlate with white matter integrity. We hypothesize that thyroid hormone treatment will be associated with an increase in fractional anisotropy, a decrease in radial diffusivity, and an increase in the myelin water fraction (markers of improved myelination) that will correlate with improvements in cognition and mood ratings. If successful, this will be the first demonstration of improved white matter integrity with thyroid hormone replacement and pave the way for therapies designed to restore structural brain connectivity.

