3.0 Objectives/Aims

The purpose of this proposed multidisciplinary, translational pilot study is to examine changes in white matter integrity using complementary neuroimaging techniques: high angular diffusion tensor imaging (HARDI) and multi-component relaxometry (MCR), in a population of participants clinically indicated to receive thyroid hormone for hypothyroidism. We will scan patients with hypothyroidism when they initiate treatment to determine baseline levels of white matter integrity and then rescan them three months and six months after starting thyroid hormone treatment to determine changes in white matter integrity. Given our sensitive and specific biomarkers of myelin integrity, we hypothesize that thyroid hormone treatment will be associated with an increase in white matter cohesion, i.e., fractional anisotropy as measured by HARDI, white matter microstructure as measured by HARDI (radial diffusivity), and MCR markers of improved myelination (myelin water fraction). In addition, we hypothesize that increases in white matter integrity will be correlated with improvements in cognition and mood. If successful, this will be

the first demonstration of improved white matter integrity with thyroid hormone replacement and pave the way for reparative therapies designed to restore structural brain connectivity.

Specific Aim 1: To measure white matter integrity at the initiation of thyroid hormone replacement and after euthyroid status using HARDI

Hypothesis 1: Participants diagnosed with hypothyroidism that become euthyroid will show improved white matter integrity measured by increasing fractional anisotropy and decreasing radial diffusivity.

Specific Aim 2: To measure white matter integrity at the initiation of thyroid hormone replacement and after euthyroid status using multicomponent relaxometry

Hypothesis 2: Participants diagnosed with hypothyroidism that become euthyroid will show improved white matter integrity measured by increasing myelin water fraction

Specific Aim 3: To correlate changes in white matter integrity with improvement in cognition and mood

Hypothesis 3: Improvement in white matter integrity will be positively correlated with cognitive function indicated by faster psychomotor processing speeds and improved executive function and with mood measured with lower depression severity ratings

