6.0 Study Design and Procedures

All participants will be treated for their hypothyroidism according to the standard of care as reflected in recent guidelines from the American Thyroid Association (27). As part of the initial screening, after informed consent is obtained, all participants will receive the following clinical tests/instruments: 1) The Cumulative Illness Rating Scale (CIRS-G;(28)); 2) The Cerebrovascular Risk Factor Scale (CVRF (29)); (stroke risk factor)

developed by the American Heart Association; 3) Patient Health Questionnaire (PHQ-9) (30)); 4) The Inventory of Depressive Symptomatology (IDS-C/IDS-SR;(31)); 5) the Montreal Cognitive Assessment (MoCA (32)); 6) Relevant laboratory studies such as complete and differential blood counts, serum chemistry, thyroid function tests; 7) A brief neuropsychological protocol focused on cognitive domains of executive function, attention, and psychomotor processing (33). *Thyroid Status Assessment:* All participants will have blood work done to obtain thyroid functions tests (TFTs): thyroid stimulating hormone (TSH), Free T4, T3, anti-thyroglobulin and anti-thyroid peroxidase (TPO) antibodies. All participants will receive *the same treatment* (levothyroxine, a synthetic T4 hormone replacement) at a dose that will be titrated using serum thyrotropin (TSH) levels as a goal, according to the American Thyroid Association Task Force recommendations (27). *Behavioral Assessment:* Depression severity will be assessed with the PHQ-9 and the IDS. Global cognitive function will be measured with the MoCA. Executive function, attention and processing speed will be assessed using the following tests from the NIH Toolbox: Dimensional Change Card Sort Test, Flanker Inhibitory Control and Attention Test and the Pattern Comparison Processing Speed Test (33). These tests have been shown to have good test-retest reliability and standardized effect sizes for practice effects (34). We will examine whether performance improvements at subsequent assessment time points exceed what would be expected due to practice effects.

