All assessments will be completed at baseline (within one week of initiating treatment), 3 months follow-up and 6 months follow-up (Table 1). PHQ-9 will be administered biweekly in between behavioral/MRI sessions. It is important to note that since levothyroxine has a long half-life (6-7 days), measurements within one week are appropriate for baseline assessments. Additionally due to this long half-life, there are no acute effects of treatment that would be missed at baseline. Assessment time points at 3 months and 6 months were chosen based on preclinical and clinical studies. DTI measures normalized in the aforementioned animal studies 3 months after TH administration (4). In clinical settings, patients might require several dose adjustments to achieve the thyrotropin goal. The usual dose adjustment intervals used in clinical

practice are 6-8 weeks. In a study by Duyff et al. evaluating the neuromuscular findings in thyroid dysfunction, hypothyroid patients reached biochemical euthyroidism in an average of 19 weeks (range 7 - 41 weeks) (35). Most studies to show improvement in mood and/or cognition had a follow-up time of 6 months (24).

Baseline	3 months	6 months
TFTs	TFTs	TFTs
Behavioral assessment	Behavioral assessment	Behavioral assessment
MRI	MRI	MRI

Table 1. Timeline for clinical, behavioral and neuroimaging assessments

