9.0 Data Analysis

Statistical Analysis: The initial analysis will be descriptive and will characterize the study groups in terms of study variables such as age, gender, education, and measures of overall medical burden etc. Categorical variables, nominal and ordinal, will be summarized by frequencies. Continuous variables will be summarized by the mean, standard deviation, 95% confidence intervals, median, and range. Where continuous variables cannot reasonably be considered to be

normally distributed, transformations (e.g. log, square root, or cube root transformation for skewed data) to achieve a normal distribution will be explored. Care must be taken to avoid placing too much emphasis on chance associations. As noted below, both unadjusted and false discovery rate p-levels will be reported basing the adjustment on the numbers of tests performed within each area. Specific Aims 1 and 2 will be analyzed using a repeated-measures analysis of variance (ANOVA) with FA, RD, and MWF as dependent variables. Specific Aim 3 will be analyzed using bivariate correlations and partial correlations (controlling for age) between changes in FA, RD, and MWF and changes in executive function and processing speed performance scores.

Sample Size/Statistical Design: There will be a total of 30 participants by the end of the study period. Data from this initial sample will be used for power calculations to determine the appropriate sample size for future studies.

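### Aims 1 and 2 are tested by visit alone, so a significant change cannot by itself be credited to thyroid hormone replacement

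*Combined protocol and SAP*

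**What the plan says.** The design has one treated group. Section 6.0 states: "All participants will receive *the same treatment* (levothyroxine, a synthetic T4 hormone replacement) at a dose" titrated to TSH. No comparison group is described; Section 9.0 speaks of groups in the plural, but only one is defined.

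On timing, Section 6.0 says: "All assessments will be completed at baseline (within one week of initiating treatment), 3 months follow-up and 6 months follow-up". Table 1 lists thyroid function tests beside MRI at each of the three visits. The same section cites a study in which hypothyroid patients reached biochemical euthyroidism after 19 weeks on average, with a range of 7 to 41 weeks.

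Hypothesis 1 in Section 3.0 reads: "Participants diagnosed with hypothyroidism that become euthyroid will show improved white matter integrity", and Hypothesis 2 is framed in the same way for myelin water fraction.

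The analysis in Section 9.0 is: "Specific Aims 1 and 2 will be analyzed using a repeated-measures analysis of variance (ANOVA) with FA, RD, and MWF as dependent variables". It names no between-subject factor, covariate, euthyroid indicator or scanner-stability check, and does not restrict the analysis to participants who become euthyroid. Sections 1.0 and 3.0 both say that, if the study succeeds, "this will be the first demonstration of improved white matter integrity with thyroid hormone replacement".

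**The concern.** With one group and no covariate, the ANOVA asks only whether the mean of each measure differs between visits. It does not ask whether the change follows thyroid status, which is what Hypotheses 1 and 2 are about. Any influence that moves all participants' images in the hypothesised direction (FA up, RD down, MWF up) between baseline and six months would produce the same result as a treatment effect. Scanner drift is the obvious example.

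The protocol recognises this type of problem for cognition: Section 6.0 will check whether cognitive gains exceed practice effects. Nothing equivalent is planned for the imaging measures that carry Aims 1 and 2. At stake is whether the conclusion in Sections 1.0 and 3.0 can be drawn from the planned analysis, when data that bear on it more directly are already being collected.

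**Working it through.** **Inputs.** From the documents: one arm, three visits, and "There will be a total of 30 participants by the end of the study period". Section 9.0 gives no alpha, effect size, SD, dropout or power, and defers power to later studies, so there is no planned figure to reproduce. Assumed here: two-sided 0.05, complete data, and a non-thyroid shift *d* in units of the SD of the baseline-to-six-month change. The documents give no value for *d*, so a range is shown.

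**1. Does the model address the hypotheses?** Three months is about 52/4 = 13 weeks and six months about 52/2 = 26 weeks. Against the cited range of 7 to 41 weeks, some participants would be euthyroid by the first follow-up scan and some would still not be at the last. Thyroid status would thus differ between people at the same visit. The visit-only model averages over that difference.

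**2. Paired t test on the six-month change, no thyroid effect.** The noncentrality is *d*√30 with 29 df and critical value 2.045.

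| Assumed shift *d* | *d*√30 | Probability of p < 0.05 |
|---|---|---|
| 0.20 | 1.095 | 0.185 |
| 0.37 | 2.027 | 0.500 |
| 0.50 | 2.739 | 0.754 |

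**3. The planned three-visit ANOVA.** Assume a linear shift (means 0, *d*/2, *d*) and compound symmetry. With the SD of change set to 1, the residual variance is 1/2. The noncentrality is 30 × (*d*²/4 + *d*²/4) ÷ (1/2) = 30*d*², on 2 and 58 df.

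| Assumed shift *d* | 30*d*² | Probability of p < 0.05 |
|---|---|---|
| 0.20 | 1.20 | 0.145 |
| 0.37 | 4.11 | 0.41 |
| 0.50 | 7.50 | 0.66 |

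A simulation of 40,000 trials per value agrees: 0.144 at 0.20 and 0.666 at 0.50, nearly all in the direction of improvement. These rates are per measure. Replace the shift by a treatment effect of the same size and every number stays the same, so the test cannot tell the two apart.

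**4. What an exposure term does.** For participant *i* at visit *j*, write y_ij = a_i + v_j + βx_ij + e_ij, with x the within-person thyroid measure. A shift shared by all participants adds only to v_j and so leaves β untouched, whatever its size. In simulation with a shared drift of 0.5 SD and β = 0, the coefficient was significant in the favourable direction in 2–3% of trials (nominal 2.5%).

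**5. What it costs in power.** With visit in the model, β is estimated only from differences between people in the course of x. Take a true effect of 0.53 SD, fully mediated by free T4; the paired test has 80% power for this. Power for β depended on the assumed within-person free T4 deviation. At an SD of 0.15 of the mean six-month rise it was about 12–14%; at 0.50 it was about 77–85%, the ranges reflecting separate simulations. The documents give no such SD.

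**The case against.** The strongest reply is that this is openly a single-arm pilot in patients who need treatment anyway, that its hypotheses in Sections 1.0 and 3.0 are put as associations, and that "Data from this initial sample will be used for power calculations to determine the appropriate sample size for future studies". That stands. It is why no control arm is asked for: with 80% power, the detectable effect would rise from 0.53 SD (30 in one arm, paired) to 0.74 SD (30 v 30) or 1.06 SD (15 v 15). But the pilot label does not supply the missing link between the visit test and thyroid status.

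A reader might infer that the plan commits itself to reporting any significant visit effect as proof of a thyroid effect. The documents do not support that. The sentence is a conditional aspiration, Section 9.0 defines no success criterion, and the words can be read as improvement during replacement. Both sections do go on to therapies for restoring connectivity, which relies on attribution, so the wording is still worth limiting.

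A reader might also suspect regression to the mean. The documents give little ground for it: Sections 4.1 and 4.2 select on diagnosis and exclusions, not on FA, RD, MWF or a TSH threshold.

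Finally, the percentages are ordinary power figures for 30 pairs with drift put in place of effect, and would be the same for any before-after study of this size. That is correct; they illustrate the point and are not an estimate for this trial.

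**Conclusion.** The point holds in a limited form. The planned analysis of Aims 1 and 2 cannot separate thyroid replacement from a shared non-thyroid shift in the hypothesised direction, and it does not test Hypotheses 1 and 2 as worded, because thyroid status is measured but unused. A visit effect alone therefore does not support the statement in Sections 1.0 and 3.0.

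This follows from the structure of the model and needs no drift figure. The illustrative rates rest on an assumed drift, a 0.05 two-sided level and 30 complete participants. The documents do not show that drift is present, how large it is or which way it runs, so nothing here says that a positive result would be false.

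**What to change.** **Section 9.0.** Keep the visit test. Add a pre-specified supportive exposure-response analysis: for each of FA, RD and MWF, a mixed model with a participant effect, visit, and one thyroid measure chosen in advance (within-person free T4, log TSH, or time-varying euthyroid status). Report the coefficient with its confidence interval.

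**Sections 1.0 and 3.0.** Describe a visit effect alone as within-person change during six months of replacement. Make any thyroid-related statement in light of the exposure coefficient and its interval, without a pass/fail gate.

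**Cost.** Some rewording and one model using tests already scheduled; no extra visits or participants. The claim becomes more modest. Power for the exposure term may be low at 30 participants, so a null coefficient would not refute a thyroid effect, and a gate on it could block a true one. The term removes drift that all participants share; it does not remove person-specific confounding that tracks thyroid recovery, and the text should say so.

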2.0 Background/Scientific Rationale

Thyroid and White Matter: George Bartzokis conceptualized a number of neuropsychiatric conditions according to a “myelin model” of the brain (1). Different disorders from neurodevelopmental (schizophrenia) to neurodegenerative (Alzheimer’s disease) have been associated with disruptions in myelin. Myelin is an essential neural component for maintaining efficient neurotransmission and enhanced processing speed. There is considerable evidence from basic research studies demonstrating that thyroid hormone (TH) plays an important role in myelination, specifically oligodendrocyte proliferation and maturation. For example, it has been shown that tetraiodothyronine (T4) treatment can induce increases in myelin basic protein mRNA and protein as well as oligodendrocyte precursor cells (OPCs) in mice with experimental allergic encephalomyelitis (2). Triiodothyronine (T3) has also been shown to increase myelin basic protein mRNA levels in perinatal rat brain (3). In another study, similar effects have been demonstrated in mice where T3 restored fractional anisotropy (FA) and increased OPC expression after cuprizone-induced demyelination (4). Furthermore, T3 has been shown to promote OPC differentiation and remyelination after cuprizone–induced demyelination in rats (5). According to a recent review (6), it is hypothesized that TH promotes remyelination by binding to thyroid receptor beta in a complex with the retinoid X receptor (RXR). This complex activates a thyroid-responsive element (TRE) which serves as promoter of the Kruppel-like factor 9 (KLF9) gene. KLF-9 then promotes the maturation and differentiation of OPCs through signaling of the chemokine CXCL12 and its receptor CXCR4. Despite the evidence from preclinical studies, there have been very few studies to examine the role of thyroid hormone in myelination in clinical studies. One study in men has shown that thyroid stimulating hormone (TSH) levels significantly correlate with increased “infarct-like vascular lesions” (7). Similarly, white matter hyperintensities have been associated with thyroid gland dysfunction in migraine sufferers (8). To date, the only diffusion tensor imaging (DTI) study examining the effects of thyroid on white matter microstructure was recently conducted in premature infants. While the authors found no difference in DTI parameters for infants who received T4 supplementation compared to placebo, infants in the lowest quartile of plasma free T4 concentrations had reduced white matter integrity in the corpus callosum and right internal capsule (9).

Thyroid and Mood: The relationship between hypothyroidism and major depressive disorder was identified over a century ago (10). There are several symptoms of hypothyroidism that overlap with the clinical presentation of major depression such as psychomotor retardation,

fatigue and apathy. A recent review highlighted that poor mood is commonly reported in patients on TH replacement therapy. Psychological well-being in these patients appears to be related to thyroid function (11). Additionally, studies have shown some improvement in mood symptoms with TH replacement therapy (12-14). Further in support of this notion, in a recent neuroimaging study of patients with Hashimoto's thyroiditis, it was shown that autoimmune markers correlated functional connectivity in affective circuits (15).

Thyroid and Cognition: Thyroid dysfunction (related to both subclinical and overt hypothyroidism) is associated with a wide array of cognitive impairments (16). A recent review demonstrated that subclinical hypothyroidism is associated with cognitive decline in aging (17). More specific deficits related to the cognitive domains of memory (18, 19), executive function (20), and processing speed (21, 22) have also been reported. Furthermore, there are a few studies demonstrating improvements in executive function and attention with TH replacement therapy (23, 24). There is some controversy regarding the reliability of these findings as there have been several negative studies showing no association between thyroid status and cognitive deficits (16, 25, 26). The literature demonstrating the cognitive benefits from thyroid replacement in adults with frank hypothyroidism is sparse. This is a gap in the literature that the proposed study seeks to address by incorporating neuroimaging data from a population of adult participants with overt hypothyroidism.

3.0 Objectives/Aims

The purpose of this proposed multidisciplinary, translational pilot study is to examine changes in white matter integrity using complementary neuroimaging techniques: high angular diffusion tensor imaging (HARDI) and multi-component relaxometry (MCR), in a population of participants clinically indicated to receive thyroid hormone for hypothyroidism. We will scan patients with hypothyroidism when they initiate treatment to determine baseline levels of white matter integrity and then rescan them three months and six months after starting thyroid hormone treatment to determine changes in white matter integrity. Given our sensitive and specific biomarkers of myelin integrity, we hypothesize that thyroid hormone treatment will be associated with an increase in white matter cohesion, i.e., fractional anisotropy as measured by HARDI, white matter microstructure as measured by HARDI (radial diffusivity), and MCR markers of improved myelination (myelin water fraction). In addition, we hypothesize that increases in white matter integrity will be correlated with improvements in cognition and mood. If successful, this will be

the first demonstration of improved white matter integrity with thyroid hormone replacement and pave the way for reparative therapies designed to restore structural brain connectivity.

Specific Aim 1: To measure white matter integrity at the initiation of thyroid hormone replacement and after euthyroid status using HARDI

Hypothesis 1: Participants diagnosed with hypothyroidism that become euthyroid will show improved white matter integrity measured by increasing fractional anisotropy and decreasing radial diffusivity.

Specific Aim 2: To measure white matter integrity at the initiation of thyroid hormone replacement and after euthyroid status using multicomponent relaxometry

Hypothesis 2: Participants diagnosed with hypothyroidism that become euthyroid will show improved white matter integrity measured by increasing myelin water fraction

Specific Aim 3: To correlate changes in white matter integrity with improvement in cognition and mood

Hypothesis 3: Improvement in white matter integrity will be positively correlated with cognitive function indicated by faster psychomotor processing speeds and improved executive function and with mood measured with lower depression severity ratings

